PT	preferred term
Q1	first quartile
Q3	third quartile
RSV	respiratory syncytial virus
RT-qPCR	quantitative real time polymerase chain reaction
SAP	statistical analysis plan
SD	standard deviation

SE standard error
SOC system organ class
TEAE treatment-emergent adverse event
TFLs tables, figures, and listings
WHO World Health Organization

1. INTRODUCTION

This statistical analysis plan (SAP) describes the statistical analysis methods and data presentations to be used in tables, figures, and listings (TFLs) in the clinical study report (CSR) for Study GS-US-218-1502. This SAP is based on the study protocol Amendment 7 dated 28 March 2016 and the electronic case report forms (eCRF) for this study. The SAP will be finalized before the database finalization. Any changes made after the finalization of the SAP will be documented in the CSR.

1.1. Study Objectives

Primary Objective

- To evaluate the effect of presatovir on RSV viral load in autologous or allogeneic hematopoietic cell transplant (HCT) recipients with an acute RSV lower respiratory tract infection (LRTI)

Secondary Objectives

- To evaluate the effect of presatovir on being free of any supplemental oxygen, and rates of respiratory failure and all-cause mortality
- To evaluate the PK, safety, and tolerability of presatovir

1.2. Study Design

This is a randomized, double-blind, placebo-controlled study evaluating the effect of presatovir on efficacy, PK, safety, and tolerability in HCT recipients with RSV LRTI.

All subjects will be permitted to receive the standard of care therapy for RSV infection per their local medical practices, in addition to the investigational medicinal product (IMP).

Approximately 60 subjects will be enrolled from approximately 45 international HCT centers.

[figure not shown]
Subjects will be randomized in a 1:1 ratio to receive IMP (presatovir or placebo) and will be stratified by 2 factors:

- Supplemental O₂ requirement (≤ 2 L/min or > 2 L/min) at the time of randomization
- Treatment of current RSV infection (yes or no) with ribavirin (oral, intravenous, or aerosolized)

A single dose of 200 mg (four 50 mg tablets) of presatovir or placebo will be administered on Study Days 1, 5, 9, 13, and 17. The study will consist of the following visits: screening (Day -1), baseline/randomization/IMP administration (Day 1), optional Visit 3 (Day 3), Visit 4 (Day 5),

Visit 5 (Day 7), Visit 6 (Day 9), Visit 7 (Day 13), Visit 8 (Day 17), Visit 9 (Day 22), and end of study (Day 28). Four additional visits at Days 35, 42, 49, and 56 will only be completed for subjects who consent to the optional extended viral monitoring and test positive for RSV at Visit 9 (Day 22) (see Figure 1-1).

Figure 1-1. **Study Visits**

[figure not shown]

1.3. Sample Size and Power

Sample size calculations are based on results observed in a study that evaluated the efficacy of oral and aerosolized ribavirin treatment for preventing progression from upper to lower respiratory tract infection in hematopoietic cell transplant recipients with RSV infections (unpublished data from [name]). The sample size calculation assumes the time-weighted average change in RSV \log_{10} viral load from Day 1 to Day 9 in the placebo group will be $-1.5 \log_{10}$ copies/mL with a corresponding standard deviation (SD) of 1.75, and that 85% of the subjects will be evaluable. Based on these assumptions, with 25 subjects per group there is approximately 85% power to detect a 1.5 log difference in time-weighted average change in \log_{10} viral load between treatment groups using a 2-sided 0.05-level test. Given an evaluable rate of 85%, a total of 60 subjects will need to be randomized into the study.

Visit 5 (Day 7), Visit 6 (Day 9), Visit 7 (Day 13), Visit 8 (Day 17), Visit 9 (Day 22), and end of study (Day 28). Four additional visits at Days 35, 42, 49, and 56 will only be completed for subjects who consent to the optional extended viral monitoring and test positive for RSV at Visit 9 (Day 22) (see Figure 1-1).

Figure 1-1. Study Visits

1.3. Sample Size and Power

Sample size calculations are based on results observed in a study that evaluated the efficacy of oral and aerosolized ribavirin treatment for preventing progression from upper to lower respiratory tract infection in hematopoietic cell transplant recipients with RSV infections (unpublished data from [name]). The sample size calculation assumes the time-weighted average change in RSV \log_{10} viral load from Day 1 to Day 9 in the placebo group will be $-1.5 \log_{10}$ copies/mL with a corresponding standard deviation (SD) of 1.75, and that 85% of the subjects will be evaluable. Based on these assumptions, with 25 subjects per group there is approximately 85% power to detect a 1.5 log difference in time-weighted average change in \log_{10} viral load between treatment groups using a 2-sided 0.05-level test. Given an evaluable rate of 85%, a total of 60 subjects will need to be randomized into the study.

2. TYPE OF PLANNED ANALYSIS

2.1. Data Monitoring Committee Analyses

An external multidisciplinary Data Monitoring Committee (DMC) will review the progress of the study and perform interim reviews of safety data in order to protect subject welfare and preserve study integrity. To ensure the best interests of the participants, the DMC will recommend to the sponsor if the nature, frequency, and severity of adverse effects associated with study treatment warrant the early termination of the study, the continuation of the study, or the continuation of the study with modifications.

The DMC's role and responsibilities and the scope of analysis to be provided to the DMC are provided in a mutually agreed upon charter, which defines the DMC membership, meeting logistics, and meeting frequency.

The initial safety review occurred after approximately 25% of the planned 60 subjects were enrolled and completed Day 28 visit or discontinued the study. No additional meetings were scheduled due to the reasons specified in Section 7.7.

2.2. Final Analysis

After all subjects have completed the study, outstanding data queries have been resolved, and the data have been cleaned and finalized, the study blind will be broken and the final analysis of the data will be performed.

3. GENERAL CONSIDERATIONS FOR DATA ANALYSES

Analysis results will be presented using descriptive statistics. For categorical variables, the number and percentage of subjects in each category will be presented; for continuous variables, the number of subjects (n), mean, standard deviation (SD) or standard error (SE), median, first quartile (Q1), third quartile (Q3), minimum, and maximum will be presented.

By-subject listings will be presented for all subjects in the relevant analysis set, and sorted by subject ID number, visit date, and time (if applicable). Data collected on log forms, such as AEs, will be presented in chronological order within the subject. The treatment group to which subjects were randomized will be used in the listings. Age, sex at birth, race, and ethnicity will be included in the listings, as space permits.

3.1. Analysis Sets

Analysis sets define the subjects to be included in an analysis. Analysis sets and their definitions are provided in this section. Subjects included in each analysis set will be determined before the study blind is broken for analysis. The analysis set will be identified and included as a subtitle of each table, figure, and listing.

For each analysis set, the number and percentage of subjects eligible for inclusion, as well as the number and percentage of subjects who were excluded, will be summarized by treatment group.

A listing of reasons for exclusion from analysis sets will be provided by subject.

3.1.1. All Randomized Analysis Set

All Randomized Analysis Set includes all subjects who were randomized in the study.

3.1.2. Full Analysis Set

The Full Analysis Set (FAS) includes all randomized subjects who received at least 1 full dose of study drug, and have an RSV viral load greater than or equal to the lower limit of quantification of the RT-qPCR assay in the Day 1 nasal sample, as determined by RT-qPCR at the central lab.

This is the primary analysis set for efficacy analyses.

3.1.3. Per Protocol Analysis Set

The Per-Protocol (PP) Analysis Set includes subjects in the FAS who meet the following criteria:

- Did not violate the following major inclusion criteria (IC)
 - IC #2: Received an autologous or allogeneic HCT using any conditioning regimen
 - IC #3: Chest X-ray obtained < 48 hours prior to Screening
 - IC #4: Documented RSV in both the upper and lower respiratory tract as determined by local testing collected \leq 6 days prior to Day 1

- Did not administered invalid (eg, expired, damaged, quarantined, improperly stored) study drug
- Not be dispensed incorrect study drug (wrong bottle) or drug from another study
- Missed < 1 dose (200 mg) in the first 9 study days
- Missed < 3 nasal swab samples over the course of the study

The PP Analysis Set is the secondary analysis set for efficacy analyses.

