6.2.2. Analysis Methods for Secondary Efficacy Endpoints

In order to account for multiple hypothesis testing of endpoints, a sequential testing procedure described in Section 3.5 will be used to control the overall Type 1 error rate of 0.05 across the primary and secondary endpoints.

The FAS will be used for all summaries and analyses of secondary endpoints. All secondary endpoints will be analyzed using 2-sided tests to compare treatment differences.

The number of supplemental O₂-free days through Day 28 will be analyzed using a negative binomial model with stratification factors as covariates and an offset parameter to account for the on-study duration. Subjects who die prior to Day 28 (inclusive) or are receiving supplemental O₂ on all days of the study period are assigned 0 supplemental O₂-free days. All survivors accrue 1 supplemental O₂-free day for each day that they are both alive and on the use of supplemental O₂ less than 12 hours per 24 hours (0:00 to 23:59) when they are on study.

The proportion of subjects who develop respiratory failure requiring mechanical ventilation and the proportion of subjects with all-cause mortality will be analyzed using Cochran-Mantel-Haenszel (CMH) test adjusting for the stratification factors at the 2-sided 0.05-level. The 2-sided 95% exact CI of the respiratory failure rate or mortality rate based on the Clopper-Pearson method will be provided for each treatment group. In the case of a small number of events, the exact method will be used.

[figure not shown]

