6.2.3. Sensitivity Analysis for Secondary Efficacy Endpoints

Sensitivity analyses of the secondary efficacy endpoints, the number of supplemental O₂-free days through Day 28, the proportion of subjects who develop respiratory failure requiring mechanical ventilation through Day 28, and the proportion of subjects with all-cause mortality through Day 28, will be performed in the PP analysis set.

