12.3. Listings

Listing	Title	Analysis Set
16.1.6	Subjects Who Received Study Drug from Specific Batches	Safety Analysis Set
16.1.7	Randomization Schema and Codes	All Randomized Analysis Set
16.2.1.1	Subject Profiles	All Randomized Analysis Set
16.2.1.2	Enrollment	All Randomized Analysis Set
16.2.1.3	Subject Disposition	All Randomized Analysis Set
16.2.1.4	Reasons for Screen Failure	Subjects Screened but Not Enrolled
16.2.2.1	Eligibility Criteria Deviations	All Randomized Analysis Set
16.2.2.2	Important Protocol Deviations	All Randomized Analysis Set
16.2.2.3	Randomization Stratification Discrepancies Between IWRS and Clinical Database	All Randomized Analysis Set
16.2.2.4	Subjects who Received Incorrect Study Drug	All Randomized Analysis Set
16.2.3.1	Subjects Excluded from Any Analysis Set	All Randomized Analysis Set
16.2.3.2	Subjects Who were in the Full Analysis Set but Excluded from the Per Protocol Analysis Set	Full Analysis Set
16.2.4.1	Demographics	All Randomized Analysis Set
16.2.4.2	Baseline Characteristics	All Randomized Analysis Set
16.2.4.3.1	Hematopoietic Cell Transplant Medical History	All Randomized Analysis Set
16.2.4.3.2	Medical History	All Randomized Analysis Set
16.2.4.4.1	Prior and Concomitant Medications	All Randomized Analysis Set
16.2.4.4.2	Prior and Concomitant Ribavirin	All Randomized Analysis Set
16.2.5.1	Study Drug Administration	All Randomized Analysis Set
16.2.5.2	Subjects Who Prematurely Discontinued Study Drug	All Randomized Analysis Set
16.2.5.3	Study Drug Accountability	All Randomized Analysis Set
16.2.5.4	Plasma Pharmacokinetic Sampling Details and Concentrations	PK Analysis Set
16.2.6.1	Viral Load Measurements	Full Analysis Set
16.2.6.2	Hospitalizations and ICU	Full Analysis Set
16.2.6.3	Oxygen Saturation	Full Analysis Set
16.2.6.4	Supplemental Oxygen	Full Analysis Set
16.2.6.5	Supplemental Oxygen Use Prior to RSV Infection	Full Analysis Set
16.2.6.6	Mechanical Ventilation	Full Analysis Set
16.2.6.7	Healthcare Related Efficacy Endpoints	Full Analysis Set
16.2.7.1	All Adverse Events	Safety Analysis Set

Listing	Title	Analysis Set
16.2.7.2.1	Deaths	All Randomized Analysis Set
16.2.7.2.2	Adverse Events Leading to Death	Safety Analysis Set
16.2.7.3	Serious Adverse Events	Safety Analysis Set
16.2.7.4.1	Adverse Events with Severity of Grade 3 or Higher	Safety Analysis Set
16.2.7.4.2	Adverse Events with Severity of Grade 2 or Higher	Safety Analysis Set

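### The Per Protocol criteria do not exempt doses and swabs due after death, so the PP analyses of mortality and O2-free days can exclude subjects because of the outcome analysed

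*SAP*

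**What the plan says.** Section 3.1.3 builds the PP set from the FAS. Two of its criteria concern completeness: "Missed < 1 dose (200 mg) in the first 9 study days" and "Missed < 3 nasal swab samples over the course of the study". The SAP does not define a missed dose or swab, and says nothing about those falling due after a subject has died.

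Section 6.2.2 makes the FAS the main set for the secondary endpoints: "The FAS will be used for all summaries and analyses of secondary endpoints". It also gives 0 supplemental O2-free days to anyone who dies by Day 28. Section 6.2.3 then repeats all three secondary endpoints in the PP set as sensitivity analyses. It names O2-free days and respiratory failure, and ends with "the proportion of subjects with all-cause mortality through Day 28, will be performed in the PP analysis set". The corresponding tables in section 12.1 are 15.9.2.1.2, 15.9.2.2.2 and 15.9.2.3.2.

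On set assignment, section 3.1 states: "Subjects included in each analysis set will be determined before the study blind is broken for analysis". It also promises a summary of exclusions by treatment group and says: "A listing of reasons for exclusion from analysis sets will be provided by subject". Listing 16.2.3.2 is titled "Subjects Who were in the Full Analysis Set but Excluded from the Per Protocol Analysis Set".

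**The concern.** A swab-completeness rule that runs to the end of the study can only be met in full by someone alive to be swabbed. If swabs due after death count as missed, the rule selects on survival, and the selected set is then used to estimate mortality. For O2-free days the same rule removes subjects whose score is 0 because they died. The dose rule acts in the same way over a shorter window. For respiratory failure the link is only indirect: a ventilated subject may be harder to dose or swab, or may die, but ventilation does not itself remove scheduled swabs.

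The PP tables are meant as a check on the FAS results. If many of the deaths can be taken out of them, agreement or disagreement with the FAS says little.

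**Working it through.** The SAP gives no figure on this point to reproduce, so the check applies the written criteria to the written schedule.

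**Inputs from the SAP**
- Doses: Days 1, 5, 9, 13 and 17 (section 1.2). Those in the first 9 days are Days 1, 5 and 9. FAS membership already requires one full dose.
- Nasal swabs after Day 1, leaving out optional Day 3: Days 5, 7, 9, 13, 17, 22 and 28 (Appendix 1).
- Limits: no missed dose in the first 9 days; at most 2 missed swabs (section 3.1.3).

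**Reading applied:** nominal visit days, swabs counted by visit, no other dose or swab missed, and items due after death counted as missed.

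**Dose rule.** A death on Days 2 to 8 leaves the Day 9 dose untaken. That is 1 missed dose, so the subject is excluded.

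**Swab rule**
- Death on Day 16: Days 17, 22 and 28 not obtained, 3 missed, excluded.
- Death on Days 17 to 21, after the Day 17 visit: Days 22 and 28 not obtained, 2 missed, retained.
- Death on Days 22 to 27, after the Day 22 visit: Day 28 not obtained, 1 missed, retained.

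The swab rule therefore excludes every death before the Day 17 visit. Deaths that fail the dose rule are a subset of these, so the two shares below must not be added.

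**Share of deaths removed.** The SAP gives no death timing. Assume deaths are uniform over Days 2 to 28, which is 27 days:
- Dose rule, Days 2 to 8: 7/27 = 26%.
- Swab rule, Days 2 to 16: 15/27 = 56%.

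**Direction.** Take 25 per group, the evaluable number in section 1.3, and assume 5 and 2 deaths. The FAS difference is 5/25 - 2/25 = 12.0 points. With k1 and k2 deaths excluded and no survivors excluded, the PP difference is (5 - k1)/(25 - k1) - (2 - k2)/(25 - k2).
- k1 = 1, k2 = 2: 4/24 - 0/23 = 16.7 points, larger than in the FAS.
- k1 = 3, k2 = 1: 2/22 - 1/24 = 4.9 points, smaller than in the FAS.

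These counts are illustrative. They show only that the distortion can go either way, depending on when deaths occur in each arm.

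**With the definition changed.** If only doses and swabs due while the subject was alive and on study can be missed, no day of death from Day 1 to Day 28 causes exclusion by itself.

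**The case against.** The strongest reply is that a dose or swab is ordinarily missed when it was due and not obtained, and nothing is due from a subject who has died. On that reading no death causes exclusion. This stands as a possible reading, and it is why the conclusion is that the criteria can exclude deaths, not that they must. The SAP does not state it, however, and the phrase about the whole course of the study points the other way.

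Second, any PP set selects on events after randomization, and requiring the doses up to Day 9 is a conventional minimum-exposure rule that matches the primary endpoint's window. This has some force for the dose rule. It does not justify a swab rule running to Day 28 for endpoints that use no swab data.

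Third, the sets are fixed before unblinding, and exclusions are summarized by arm (Table 15.8.5) and listed. Blinded assignment prevents choices informed by treatment, but not selection by outcome. The summary and listings would show what was removed, but would leave the PP tables as they are.

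A reader might also infer larger losses. Footnote f of Appendix 1 takes two samples per visit, one per nostril. Counting single samples would move the swab cut-off to deaths through Day 21 (20/27 = 74%). Counting a skipped Day 3 visit as well would move it to Day 27 (26/27 = 96%). The SAP does not rule these readings out, but they are the less natural ones. Section 3.1.2 speaks of a single Day 1 nasal sample, a limit of fewer than 3 single swabs would allow only one fully missed visit, and Day 3 is expressly optional for subjects who are not hospitalized. The headline size should not rest on them.

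**Conclusion.** The concern holds as a gap in the PP definition that matters because of how section 6.2.3 uses the set. Read literally, with swabs counted by visit, deaths before the Day 9 dose fail the dose rule and deaths before the Day 17 visit fail the swab rule. Membership of the set can then depend on the endpoint analysed in it.

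The size is undetermined. The shares of 26% and 56% rest on uniform death timing over Days 2 to 28 and on no other missed doses or swabs. The direction is also undetermined. A reader might infer that the PP difference must shrink towards zero, but the documents do not support this, because they give neither the number nor the timing of deaths by arm.

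The effect is confined to Tables 15.9.2.1.2 and 15.9.2.3.2, and indirectly 15.9.2.2.2. A reader might infer that the trial's confirmatory results are at risk. They are not: the secondary endpoints are analysed in the FAS, and the gatekeeping sequence of section 3.5 does not use the PP results. The point is worth correcting because it is cheap to correct, but it is not a serious threat to the trial's conclusions.

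**What to change.** - **Section 6.2.3:** do not apply the swab-completeness criterion to the PP analyses of O2-free days, respiratory failure and mortality, which use no swab data.
- **Section 3.1.3:** define a missed dose or swab as one that was due while the subject was alive and on study and was not taken or obtained. Count swabs by visit. State that a non-hospitalized subject who does not attend the optional Day 3 visit has not missed a swab.

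The definition should apply alike to deaths and withdrawals. Exempting deaths alone would keep subjects who died with doses or swabs outstanding while dropping those who withdrew with the same ones outstanding. Membership would still depend on outcome, and PP mortality would tend to be inflated.

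The cost is a few lines of SAP text before the blind is broken, and one extra PP flag, because the set for the clinical endpoints would differ from the set for viral load. No new data are needed. The downside is that some subjects with short follow-up stay in the PP set.

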3.1.4. Safety Analysis Set

The Safety Analysis Set includes subjects who took at least 1 full dose of study drug. This is the primary analysis set for safety analyses.

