3.7. Data Handling Conventions and Transformations

In general, age (in years) on the date of the first dose of study drug will be used for analyses and presentation in listings. If an enrolled subject was not dosed with any study drug, the randomization date will be used instead of the first dosing date of study drug. For screen failures, the date the informed consent was signed will be used for age calculation. If only the birth year is collected on the eCRF, “01 January” will be used for the unknown birth day and month for the purpose of age calculation. If only birth year and month are collected, “01” will be used for the unknown birth day.

Non-PK data that are continuous in nature but are less than the lower limit of quantitation (LOQ) or above the upper LOQ will be imputed as follows:

- A value that is 1 unit less than the LOQ will be used to calculate descriptive statistics if the datum is reported in the form of “ $< x$ ” (where x is considered the LOQ). For example, if the values are reported as < 50 and < 5.0 , values of 49 and 4.9, respectively, will be used to calculate summary statistics. An exception to this rule is any value reported as < 1 or < 0.1 , etc. For values reported as < 1 or < 0.1 , a value of 0.9 or 0.09, respectively, will be used to calculate summary statistics.
- A value that is 1 unit above the LOQ will be used to calculate descriptive statistics if the datum is reported in the form of “ $> x$ ” (where x is considered the LOQ). Values with decimal points will follow the same logic as above.
- The LOQ will be used to calculate descriptive statistics if the datum is reported in the form of “ $\leq x$ ” or “ $\geq x$ ” (where x is considered the LOQ).

If methods based on the assumption that the data are normally distributed are not adequate, analyses may be performed on transformed data (eg, log-transformed data) or nonparametric analysis methods may be used, as appropriate.

Plasma concentration values that are below the limit of quantitation (BLQ) will be presented as “BLQ” in the concentration data listing. Values that are BLQ will be treated as 0 at predose time points, and one-half the value of the LOQ at post-baseline time points.

The following conventions will be used for the presentation of summary and order statistics:

- If at least 1 subject has a concentration value of BLQ for the time point, the minimum value will be displayed as “BLQ.”

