4.2.2. Adherence to Study Drug

The total number of tablets administered will be summarized using descriptive statistics.

The presumed total number of tablets administered to a subject will be determined by the data collected on the drug accountability eCRF using the following formula:

$$\begin{aligned} & \text{Total Number of Tablets Administered} \\ &= \left(\sum \text{No. of Tablets Dispensed at Study Dosing Visits} \right) \end{aligned}$$

The level of prescribed adherence to the study drug regimen will be determined by the total amount of study drug administered relative to the total amount of study drug specified by the protocol for a subject who completes treatment in the study.

The level of prescribed adherence will be expressed as a percentage using the following formula:

$$\text{Prescribed Adherence (\%)} = \left(\frac{\text{Total Amount of Study Drug Administered}}{\text{Total Amount of Study Drug Specified by Protocol}} \right) \times 100$$

Descriptive statistics for adherence (sample size, mean, SD, median, Q1, Q3, minimum, and maximum) along with the number and percentage of subjects belonging to adherence categories (eg, < 80% and $\geq 80\%$) will be provided by treatment group for the Safety Analysis Set.

No formal statistical testing is planned.

A by-subject listing of study drug administration and drug accountability will be provided separately by subject ID number (in ascending order) and visit (in chronological order).

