7.1.5. Treatment-Emergent Adverse Events

7.1.5.1. Definition of Treatment-Emergent Adverse Events

Treatment-emergent adverse events (TEAE) are defined as 1 or both of the following:

- Any AEs with an onset date on or after the study drug start date up to the Day 28, or up to 28 days if a subject withdraws early (prior to Day 28) from the study
- Any AEs leading to premature discontinuation of study drug

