7.1.6. Summaries of Adverse Events and Deaths

Treatment-emergent (TE) AEs will be summarized based on the Safety Analysis Set.

The number and percentage of subjects who experienced at least 1 TEAE will be provided and summarized by SOC and PT, and treatment group. For other AEs described below, summaries will be provided by SOC, PT, and treatment group:

- TEAE by maximum severity
- TEAEs of Grade 3 or higher (by maximum severity)
- TEAEs of Grade 2 or higher
- All TE treatment-related AEs
- All TE treatment-related AEs by maximum severity
- TE treatment-related AEs of Grade 3 or higher (by maximum severity)
- TE treatment-related AEs of Grade 2 or higher
- All TE SAEs
- All TE treatment-related SAEs
- All TEAEs leading to premature discontinuation of study drug

- All TEAEs leading to premature discontinuation of study
- All AEs leading to death (ie, outcome of death)

A brief, high-level summary of AEs described above will be provided by treatment group and by the number and percentage of subjects who experienced the above AEs. All deaths observed in the study will be also included in this summary.

Multiple events will be counted only once per subject in each summary. Adverse events will be summarized and listed first in alphabetic order of SOC and HLT within each SOC (if applicable), and then by PT in descending order of total frequency within each SOC. For summaries by severity grade, the most severe grade will be used for those AEs that occurred more than once in an individual subject during the study.

In addition to the above summary tables, all TEAEs, TE treatment-related AEs, and TE SAE will be summarized by PT only, in descending order of total frequency.

In addition, data listings will be provided for the following:

- All AEs, indicating whether the event is treatment emergent
- All AEs of Grade 3 or higher
- All AEs of Grade 2 or higher
- SAEs
- Deaths
- All AEs leading to death (ie, outcome of death)
- AEs leading to premature discontinuation of study drug
- AEs leading to premature discontinuation of study

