15.11.2.3.3.3	Treatment-Emergent Treatment-Related Adverse Events with Severity of Grade 3 or Above by Preferred Term	Safety Analysis Set
15.11.2.3.3.4	Treatment-Emergent Treatment-Related Adverse Events with Severity of Grade 2 or Above by Preferred Term	Safety Analysis Set
15.11.2.4	Treatment-Emergent Adverse Events of Interest (Cardiac Adverse Event) by System Organ Class and Preferred Term	Safety Analysis Set
15.11.3	Treatment-Emergent Adverse Events Leading to Death by System Organ Class and Preferred Term	Safety Analysis Set
15.11.4.1	Treatment Emergent Serious Adverse Event by System Organ Class and Preferred Term	Safety Analysis Set
15.11.4.2	Treatment Emergent Serious Adverse Event by Preferred Term	Safety Analysis Set
15.11.4.3.1	Treatment Emergent Treatment-Related Serious Adverse Events by System Organ Class and Preferred Term	Safety Analysis Set
15.11.4.3.2	Treatment Emergent Treatment-Related Serious Adverse Events by Preferred Term	Safety Analysis Set
15.11.4.4	Treatment-Emergent Serious Adverse Events of Interest (Cardiac Adverse Event) by System Organ Class and Preferred Term	Safety Analysis Set
15.11.5.1	Treatment-Emergent Adverse Events Leading to Premature Discontinuation of Study Drug by System Organ Class and Preferred Term	Safety Analysis Set
15.11.5.2	Treatment-Emergent Adverse Events Leading to Premature Discontinuation of Study by System Organ Class and Preferred Term	Safety Analysis Set
15.11.6.1.1	Hematology Test: Hemoglobin (g/dL) and Change from Baseline	Safety Analysis Set
15.11.6.1.2	Hematology Test: Lymphocytes ($\times 10^3/\mu\text{L}$) and Change from Baseline	Safety Analysis Set

Table Number	Title	Analysis Set
15.11.6.1.3	Hematology Test: Lymphocytes (%) and Change from Baseline	Safety Analysis Set
15.11.6.1.4	Hematology Test: Monocytes ($\times 10^3/\mu\text{L}$) and Change from Baseline	Safety Analysis Set
15.11.6.1.5	Hematology Test: Monocytes (%) and Change from Baseline	Safety Analysis Set
15.11.6.1.6	Hematology Test: Neutrophils ($\times 10^3/\mu\text{L}$) and Change from Baseline	Safety Analysis Set
15.11.6.1.7	Hematology Test: Neutrophils (%) and Change from Baseline	Safety Analysis Set
15.11.6.1.8	Hematology Test: Platelets ($\times 10^3/\mu\text{L}$) and Change from Baseline	Safety Analysis Set
15.11.6.1.9	Hematology Test: Leukocytes ($\times 10^3/\mu\text{L}$) and Change from Baseline	Safety Analysis Set
15.11.6.2.1	Chemistry Test: ALT (U/L) and Change from Baseline	Safety Analysis Set

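### The Safety Analysis Set requires one full four-tablet dose, so a subject who only ever took part of a dose appears in no planned AE table or AE listing

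*SAP*

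**What the plan says.** Section 3.1.4 sets the entry rule: "The Safety Analysis Set includes subjects who took at least 1 full dose of study drug". Full dose is not defined separately, but section 1.2 gives the unit: "A single dose of 200 mg (four 50 mg tablets) of presatovir or placebo will be administered", on Days 1, 5, 9, 13 and 17. The per-protocol criteria in 3.1.3 also put a dose at 200 mg.

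Section 7.1.5.1 defines a treatment-emergent AE by onset from the study drug start date to Day 28, or as one of "Any AEs leading to premature discontinuation of study drug". Neither limb has a full-dose condition.

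Section 7.1.6 fixes the population: "Treatment-emergent (TE) AEs will be summarized based on the Safety Analysis Set". Of the high-level AE summary it adds: "All deaths observed in the study will be also included in this summary". Section 3 confines by-subject listings to the relevant analysis set. Section 4.1 uses the Safety Analysis Set as the denominator for percentages of study drug and study discontinuation.

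**The concern.** Exposure begins with the first tablet. The treatment-emergent definition follows that logic, but the population rule does not. The SAP can therefore classify an event as treatment-emergent and then show it in no AE output.

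The exclusion can also depend on the outcome. If a subject's first dose is broken off because of an AE and no full dose follows, that AE is the reason the subject falls outside the set. The table titled "Treatment-Emergent Adverse Events Leading to Premature Discontinuation of Study Drug by System Organ Class and Preferred Term" would omit the very kind of event it is meant to display. What is at stake is the completeness of AE reporting for an exposed subject. The gatekept efficacy tests are not involved.

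**Working it through.** The SAP states no figure on this point, so there is none to reproduce. The check is a reading of the set assigned to each output, followed by simple arithmetic on scale.

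**Step 1: who is excluded.** Sections 3.1.4 and 1.2 together require four tablets on at least one dosing day. A subject who took one to three tablets and never a full dose is outside the set. Any later full dose brings the subject back in.

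**Step 2: whether their events count as treatment-emergent.** Yes. Under 7.1.5.1 the window opens at the study drug start date, and AEs that stop study drug qualify in their own right.

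**Step 3: where those events could appear.**

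| Output | Set in SAP section 12 |
|---|---|
| 28 AE tables, 15.11.2.1.1.1 to 15.11.5.2 | Safety Analysis Set, all 28 |
| 7 AE listings: 16.2.7.1, 16.2.7.2.2, 16.2.7.3, 16.2.7.4.1, 16.2.7.4.2, 16.2.7.5.1, 16.2.7.5.2 | Safety Analysis Set, all 7 |
| Deaths, Listing 16.2.7.2.1 | All Randomized Analysis Set |
| Analysis Sets, Table 15.8.5 | All Randomized Analysis Set |
| Subjects excluded from any set, Listing 16.2.3.1 | All Randomized Analysis Set |
| Study drug administration, Listing 16.2.5.1 | All Randomized Analysis Set |

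No AE table or AE listing is planned for all randomised subjects or for subjects with any exposure.

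**Step 4: discontinuation percentages.** The denominator in 4.1 excludes the subject. The subject's stop is therefore either left out or divided by a count to which the subject does not belong.

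**Step 5: the deaths row.** Section 7.1.6 puts every death in the study into the high-level summary, while Table 15.11.2.1.1.1 is labelled Safety Analysis Set. The population for that row is not stated.

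**Step 6: scale.** Inputs: 60 subjects randomised 1:1 (1.2), taken as 30 per arm; one subject only ever partly dosed (an assumption, since the SAP gives no number). Let x be the number in the arm with a given AE.

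If the omitted subject had the AE, the reported rate falls by x/30 − (x − 1)/29:

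- x = 1: 3.33% − 0% = 3.33 points
- x = 3: 10.00% − 6.90% = 3.10 points
- x = 10: 33.33% − 31.03% = 2.30 points

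If the omitted subject did not have the AE, the rate rises by x/29 − x/30, which is 0.11, 0.34 and 1.15 points for the same x. With no such subject, nothing changes.

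**The case against.** The strongest reply is that the gap is small and open to view. Section 3.1 requires excluded subjects to be counted by arm and the reasons listed by subject, so Table 15.8.5 and Listing 16.2.3.1 would disclose the exclusion. Deaths stay in the all-randomised listing, and 7.1.4 has SAEs reconciled with the safety database. Appendix 1 requires all five dosing visits to take place in hospital or clinic, and a subject must miss a full dose at every one to be affected. All of this stands, and it keeps the point minor. It does not put the AE itself into an AE table or AE listing.

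The definition may also repeat the protocol, which is not at hand. That affects how a change is documented, not whether the rule is sound.

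A reader might infer more than the SAP supports:

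- **Contradiction with 3.7.** The phrase "If an enrolled subject was not dosed with any study drug" only selects a reference date for calculating age. It is not an exposure boundary and does not conflict with 3.1.4.
- **The full-dose test cannot be applied.** Section 4.2.2 says "The presumed total number of tablets administered to a subject will be determined by the data collected on the drug accountability eCRF" and sums tablets dispensed. That formula serves adherence. Nothing makes it the test for set membership, and a study drug administration listing is planned.
- **The all-randomised listings omit the AE's details.** The SAP does not define the columns of those listings, so what they show or omit cannot be asserted.
- **Mortality and respiratory failure also need all-randomised analyses.** Those endpoints use the FAS. Such analyses would be an addition, not the correction of an error in 3.1.4.

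**Conclusion.** The point holds in a narrow form and is minor. As written, 3.1.4 leaves an exposed subject who never took a full dose out of every planned AE table and AE listing, although that subject's events can meet the SAP's own treatment-emergent definition. Because a dose can be broken off for an AE, the omission need not be independent of safety.

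The reading of the text is firm; the consequence is conditional. The number affected is not given and may be zero. With 30 per arm and one such subject who had the AE, that arm's rate is understated by about 2.3 to 3.3 points for x from 10 down to 1. The failing is in AE reporting. The SAP gives no ground for saying that events go uncollected or that deaths are lost.

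**What to change.** 1. In 3.1.4, define the Safety Analysis Set as all subjects who took any amount of study drug, determined from the study drug administration record (Listing 16.2.5.1) before the blind is broken, as 3.1 already requires for all sets.
2. Footnote Table 15.11.2.1.1.1 to say that the row for all deaths observed covers all randomised subjects.
3. If the protocol carries the full-dose definition, record the edit in 7.7 as a change from the protocol.

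The cost is one sentence, one footnote and possibly one entry in 7.7. No new table or data collection is needed for these changes. Other outputs built on the same set (exposure, laboratory, vital signs, ECG) would take the new denominator automatically. If every dosed subject took a full dose at least once, no result changes.
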